#### Table 2-2Example 2 by 2 contingency table for each reader

		New 1	Reads
		Positive	Negative
Original	Positive	a	b
Reads	Negative	с	d

**Step 2:** Based on the contingency tables described above, a simple agreement rate, i.e.  $\frac{a+d}{a+b+c+d}$  and its corresponding 95% confidence interval (Agresti A, Coull BA 1998) will be estimated based on normal approximation.

Step 3: Finally, a Cohen's kappa statistic ( $\kappa_2$ ) and its corresponding 95% confidence interval will be estimated (Cohen J 1960; Cohen J 1968; Fleiss J, Levin B, Paik MC 2003) using the formula  $\kappa_2 \pm 1.96SE$ , where  $SE = \sqrt{\frac{p_0(1-p_0)}{N(1-p_e)^2}}$  (McHugh M 2012). Let N denote the number of re-reads (N = 20), k the number of categories (k = 2),  $n_{i1}$ the number of times the original reads were assigned to i (i = 1, ..., k) and  $n_{i2}$ the number of times the re-read were assigned to i (i = 1, ..., k). Then Cohen's kappa can be calculated as  $\kappa_2 = \frac{p_0 - p_e}{1-p_e}$ , where  $p_0$  is the relative agreements among the original and re-reads ( $p_0 = \frac{a+d}{a+b+c+d}$  in Table 2-2) and  $p_e = \sum_{i=1}^k \frac{n_{i1}}{N} \frac{n_{i2}}{N}$  ( $p_e = \frac{a+b}{N} \frac{a+c}{N} + \frac{c+d}{N} \frac{b+d}{N}$  in Table 2-2). Intra-reader variability will be calculated for the SAF.

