SAP Amendment 2		Study No. CAAA405A12302

can be calculated as:  $\kappa_1 \pm 1.96 \hat{se}(\kappa_1)$ ). An additional table will be presented to show the distribution of agreements with the number (%) of scans agreed by two readers and the number (%) of scans agreed by all three readers. Inter-reader variability will be calculated for the SAF.

[F]CTT1057 scan intra-reader variability will be assessed by Cohen's Kappa ( $\kappa_2$ ) statistic. To assess the intra-reader variability, each of the three readers will re-read the same 20 randomly selected cases (with evaluable PET/CT) but each case will be presented to each reader in a random order. The readers will not reference any previous read results nor discuss any of these cases at any time during the read process. Each reader will use the same method to read the randomly presented cases as they did in the previous reads. Intra-reader agreement will first be evaluated separately for each of the 3 readers using Cohen's kappa statistic ( $\kappa_2$ ) as described below:

**Step 1:** A 2 by 2 contingency table (e.g. Table 2-2) will be calculated to summarize the frequency of concordance and discordance for patient-level positivity or negativity. The counts in the table will add up to 20 in total (i.e. a + b + c + d = 20).

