#### 5.4.2 Analysis supporting secondary objective(s)

For patient-level efficacy endpoints, their estimation and two-sided exact binomial 95% CIs will be calculated (implemented using SAS procedure FREQ with EXACT statement for one-way tables) (Clopper and Pearson 1934).

Only pelvic lymph node regions will be used to calculate region-level efficacy endpoints, and their estimation and two-sided exact binomial 95% CIs will also be calculated.

For inter- and intra-reader variability, 95% CIs will be calculated based on normal approximation with details given in Section 2.6.2.

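### The planned 95% CI for intra-reader kappa has zero width when a reader agrees on all 20 re-reads, and the SAP has no rule for that case or for undefined kappa

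*SAP*

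**What the plan says.** Intra-reader agreement is a secondary endpoint (Protocol Table 2-1, SAP Table 1-1). SAP 2.6.2 states that "each of the three readers will re-read the same 20 randomly selected cases", and patient-level positive/negative calls are cross-tabulated for each reader in a 2×2 table of 20.

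- **Step 2** gives the simple agreement rate p0 = (a+d)/20 and its "corresponding 95% confidence interval (Agresti A, Coull BA 1998) will be estimated based on normal approximation".
- **Step 3** gives kappa = (p0 − pe)/(1 − pe), with limits kappa ± 1.96 SE and SE = sqrt(p0(1−p0)/(N(1−pe)²)). The sample size is fixed in the text: "Let N denote the number of re-reads (N = 20), k the number of categories (k = 2".

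SAP 5.4.2 repeats the choice: "For inter- and intra-reader variability, 95% CIs will be calculated based on normal approximation". The same section uses Clopper-Pearson limits for the patient-level diagnostic proportions. Neither section says what to report when p0 = 1 or pe = 1. No expected kappa, positivity rate or precision target is stated.

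**The concern.** The Step 3 standard error is a Wald standard error for p0, rescaled by 1/(1−pe). Wald intervals fail when the observed proportion reaches 1. That is a realistic result here: n is only 20, and a competent reader should nearly always repeat the same call. The clinical study report could then state kappa 1.00 (95% CI 1.00–1.00), which claims certainty from 20 scans.

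An undefined kappa is also plausible. Every participant has biopsy-proven high-risk cancer (Protocol 5.1), and one visually positive lesion in any region makes the patient positive (Protocol 4.1). A reader could therefore call all 20 scans positive both times. Without a rule, the handling would be chosen after the result is seen.

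**Working it through.** **Inputs.** N = 20, k = 2 and the formulas come from SAP 2.6.2. The SAP gives no kappa figure to reproduce. Positivity q and true kappa κ below are assumptions, with equal marginals for the two reads. The value 0.63 equals the assumed patient-level sensitivity in SAP 3.1, but it is not a documented share of scans read positive.

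**1. Perfect agreement, both categories present.** For 14 positive and 6 negative on both reads: p0 = 1, pe = 0.7² + 0.3² = 0.58, kappa = 0.42/0.42 = 1, SE = sqrt(1×0/20)/0.42 = 0. The CI is 1.00–1.00. The splits 10/10, 16/4, 18/2 and 19/1 give the same interval.

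**2. All reads in one category.** pe = 1, so kappa and SE are both 0/0.

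**3. One disagreement.** Table a,b,c,d = (10,1,0,9): p0 = 0.95, pe = (11×10 + 9×10)/400 = 0.50, kappa = 0.45/0.50 = 0.90, SE = sqrt(0.95×0.05/20)/0.50 = 0.0975. The CI is 0.71–1.09: not collapsed, but its upper limit is impossible.

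**4. Chance of a zero-width interval.** The cell probabilities are p11 = q² + κq(1−q), p00 = (1−q)² + κq(1−q), p10 = p01 = q(1−q)(1−κ). The probability of agreement on one case is 1 − 2q(1−q)(1−κ). For q = 0.63 and κ = 0.9 this is 1 − 2×0.63×0.37×0.1 = 0.95338, and 0.95338^20 = 0.385. The all-one-category part is below 0.0001. Coverage therefore cannot exceed about 1 − 0.385 = 0.615.

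**5. Exact coverage.** All 2×2 tables with total 20 were enumerated. Coverage is conditional on kappa being defined.

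| q | κ | P(zero width) | P(undefined) | Coverage, SAP interval | Coverage, Wilson-rescaled |
|---|---|---|---|---|---|
| 0.63 | 0.8 | 0.141 | <0.001 | 0.853 | 0.96 |
| 0.63 | 0.9 | 0.385 | <0.001 | 0.613 | 0.93 |
| 0.8 | 0.8 | 0.261 | 0.005 | 0.735 | 0.95 |
| 0.9 | 0.8 | 0.399 | 0.081 | 0.565 | 0.95 |
| 0.9 | 0.9 | 0.596 | 0.099 | 0.338 | 0.91 |
| 0.95 | 0.9 | 0.502 | 0.324 | 0.257 | 0.88 |

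Among tables with a non-zero SE, the SAP interval covers at least 0.90 in every cell for q = 0.5–0.95 and κ = 0.6–0.9, and at least 0.99 for κ = 0.8–0.9. At κ = 0.6 and q = 0.5 overall coverage is 0.92, so the shortfall there is modest.

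**6. Wilson-rescaled limits.** At 20/20 the Wilson limits for p0 are 0.839–1.000. With pe = 0.53, the lower kappa limit is (0.839 − 0.53)/0.47 = 0.66, so the interval is 0.66–1.00. For the table in step 3, the Wilson limits for 19/20 are 0.764–0.991, giving (0.764 − 0.50)/0.50 = 0.53 to (0.991 − 0.50)/0.50 = 0.98.

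**The case against.** The strongest reply is that little depends on this interval. Intra-reader kappa has no hypothesis, threshold or decision rule. Study success rests on the two co-primary lower bounds and the two-of-three-reader rule in SAP 2.5.2. Kappa will also not stand alone: SAP 2.6.2 plans each reader's 2×2 table and an agreement rate with its own CI. That is right, and it limits the importance of the point. It does not make a 1.00–1.00 interval for kappa correct.

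A reader might infer that Step 2 has the same fault. As cited, it does not: the Agresti-Coull interval at 20/20 is about 0.81–1.00. The phrase normal approximation could be read as plain Wald, which would collapse, so a clarification is useful. Asking for Clopper-Pearson limits there because the SAP uses them elsewhere would only be a preference.

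A reader might also infer that the kappa interval is too narrow whenever agreement is good. It is not. At 19/20 it is wide and overshoots 1, and once the zero-width cases are set aside coverage is at least 0.90. The low coverage figures at high kappa are almost entirely the probability of 20/20 restated; they do not show a second defect.

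Finally, the positivity and kappa values are assumed. The collapse at 20/20 is algebraic and needs no assumption; how often it occurs does.

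**Conclusion.** The point holds for Step 3 of SAP 2.6.2 and its restatement in 5.4.2. As written, 20/20 agreement with both categories present must produce a 95% CI of 1.00–1.00, and all reads in one category must produce no kappa at all. If true kappa is 0.8–0.9 and positivity 0.63–0.9, coverage of the nominal 95% interval lies between 34% and 85%, and each reader has a 14% to 60% chance of a zero-width interval. At positivity 0.9 and kappa 0.6–0.9, kappa is undefined in 5–10% of samples. These figures assume equal marginals for the two reads and values that the documents do not give.

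The consequence is misstated precision for a descriptive secondary endpoint. Nothing here supports the inference that the co-primary conclusions or the kappa point estimates are wrong.

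**What to change.** Change Step 3 only, and align SAP 5.4.2:

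- Compute Wilson 95% limits (pL, pU) for p0. Report kappa limits (pL − pe)/(1 − pe) and (pU − pe)/(1 − pe), stating that the estimated pe is treated as fixed.
- If pe = 1, state that kappa is not estimable and report the agreement rate with its CI.
- In Step 2, keep the method and say explicitly that the cited Agresti-Coull interval is used, not a plain Wald interval.

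The upper kappa limit then cannot exceed 1. Coverage is about 91–97% for positivity 0.63–0.9 and kappa 0.7–0.9. It falls to 88% at positivity 0.95 and kappa 0.9, where the present interval covers 26%.

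The cost is a sentence or two in the SAP and a few lines of code. Re-reads, reader workload and point estimates do not change. The downside is wider intervals, and very wide ones when negatives are rare: 20/20 agreement with 19 positives and 1 negative has pe = 0.905 and a lower limit of (0.839 − 0.905)/0.095, about −0.7. That reflects how little such a sample says about kappa.

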#### 2.6.3 Handling of intercurrent events

Though no secondary estimands are defined for the study, intercurrent events defined in the primary estimands will impact secondary endpoints analysis. Thus they will be handled in the same way as in primary estimands analyses. Participants who receive the investigational

Novartis	Confidential	Page 27 of 43
SAP Amendment 2		Study No. CAAA405A12302

imaging agent [F]CTT1057 but do not undergo/complete the [F]CTT1057 PET/CT scan for any reasons (e.g. drop out, PET camera failures, etc) will not be used for the secondary efficacy endpoint analysis, but safety data for these participants will be collected after the administration of the investigational imaging agent and will be summarized.

#### 2.6.4 Handling of missing values not related to intercurrent event

This is a diagnostic study, where the secondary endpoints are calculated on the basis of a onetime imaging assessment. Missing data will not be imputed.

#### 2.6.5 Sensitivity analyses

No sensitivity analyses are planned for the secondary endpoints.

#### 2.6.6 Supplementary analyses

No supplementary analyses are planned for the secondary endpoints.

### 2.8 Safety analyses

All safety analyses will be based on the safety set.

### 2.8.1 Adverse events (AEs)

Adverse events are coded using MedDRA terminology. The latest MedDRA version used for reporting will be specified in the CSR and as a footnote in the applicable tables/listings. AEs will be assessed according to the Common Terminology Criteria for Adverse Events (CTCAE) version 5.0. AE summaries will include all AEs that started or worsened during the on-treatment period. (See Section 2.1.1) All AEs that started or worsened within 14 days after the [F]CTT1057 dose, and adverse events that were reported as related to [F]CTT1057 irrespective of time of onset will be regarded as treatment emergent AEs.

Novartis	Confidential	Page 29 of 43
SAP Amendment 2		Study No. CAAA405A12302

AEs will be summarized by the number and percentage of participants having at least one AE, having at least one AE in each primary system organ class (SOC) and for each preferred term (PT) using MedDRA coding. A participant with multiple occurrences of an AE will be counted only once in the respective AE category. A participant with multiple CTCAE grades for the same preferred term will be summarized under the maximum CTCAE grade recorded for the event. AE with missing CTCAE grade will be included in the 'All grades' column of the summary tables.

In AE summaries, the primary system organ class will be presented alphabetically and the preferred terms will be sorted within primary SOC in descending frequency.

The following adverse event summaries will be produced: overview of all adverse events and deaths (number and % of participants who died, with any AE, any SAE, any dose change, drug withdrawn, etc.), AEs by SOC and PT, by relationship (all AEs and AEs related to study treatment), seriousness (SAEs and non-SAEs), leading to treatment discontinuation, leading to dose change, and leading to fatal outcome. In addition, a summary of serious adverse events with number of occurrences will be produced (an occurrence is defined as >1 day between start and prior end date of record of same preferred term). To help evaluate the impact of the COVID-19 on the safety, the incidence of COVID-19 related adverse event preferred terms will be presented. All COVID-related AEs will be included in the listings.

For the legal requirements of ClinicalTrials.gov and EudraCT, two required tables for ontreatment emergent adverse events which are not serious adverse events with an incidence of greater than 5% and on-treatment emergent serious adverse events and SAE suspected to be related to study treatment will be provided by SOC and PT for the SAF.

- If for the same participant, several consecutive AEs (irrespective of study treatment causality, seriousness and severity) occurred with the same SOC and PT: a single occurrence will be counted if there is ≤ 1 day gap between the end date of the preceding AE and the start date of the consecutive AE
- more than one occurrence will be counted if there is > 1 day gap between the end date of the preceding AE and the start date of the consecutive AE

For occurrence, the presence of at least one SAE / SAE suspected to be related to study treatment / non SAE has to be checked in a block e.g., among AE's in  $a \le 1$  day gap block, if at least one SAE is occurring, then one occurrence is calculated for that SAE.

The number of deaths resulting from SAEs suspected to be related to study treatment and SAEs irrespective of study treatment relationship will be provided by SOC and PT.

All AEs collected in the AE (e)CRF page will be listed along with the information collected on those AEs, e.g. AE relationship to study drug, AE outcome, etc. All AEs, deaths, and serious adverse events (including those from the pre- and post-treatment periods) will be listed and those collected outside of the on-treatment period will be flagged.

#### 2.8.1.1 Safety topics of interest / grouping of AEs

A safety topic of interest (STI) is a grouping of adverse events that are of scientific and medical concern specific to the tracer [F]CTT1057. These groupings are defined using MedDRA terms,

Novartis	Confidential	Page 30 of 43
SAP Amendment 2		Study No. CAAA405A12302

SMQs (standardized MedDRA queries), HGLTs (high level group terms), HLT (high level terms) and PTs (preferred terms). Customized SMQs (Novartis MedDRA queries, NMQ) may also be used. A NMQ is a customized group of search terms which defines a medical concept for which there is no official SMQ available or the available SMQ does not completely fit the need. It may include a combination of single terms and/or an existing SMQ, narrow or broad. STI will be defined at the project level and may be regularly updated. The grouping of AEs in STI according to project standards will be specified in the electronic Case Retrieval Sheet (eCRS). For each specified STI, the number and percentage of participants with at least one event of the STI occurring during on-treatment period will be summarized.

STIs will be summarized by grade, SAE, relationship, leading to treatment discontinuation, leading to dose adjustment/interruption, hospitalization, death etc. A listing of all grouping levels down to the MedDRA preferred terms used to define each STI will be generated. All the analyses will be carried out for the SAF.

### 2.8.2 Deaths

Two separate summaries, one for on-treatment and the other for all deaths (including posttreatment deaths) will be produced, by system organ class and preferred term. The number of deaths resulting from SAEs suspected to be related to study treatment will also be summarized. See details given in Section 2.8.1.

All deaths will be listed, post-treatment deaths will be flagged. A separate listing of deaths prior to starting treatment will be provided for all screened participants.

#### 2.8.3 Laboratory data

Laboratory data from all sources (central and local laboratories) will be combined for the analysis. The summaries will include all assessments available for the lab parameter collected prior to (baseline) and during the on-treatment period (14 + 3 day-window) after the study treatment administration.

All laboratory data will be listed by participant and visit/time and if normal ranges are available abnormalities will be flagged. Summary statistics will be provided by visit/time. Shift tables using the low/normal/high/ (low and high) classification will be used to compare baseline to the worst on-treatment value.

Grading of laboratory values will be assigned programmatically as per National Cancer Institute (NCI) CTCAE version 5.0. The calculation of CTCAE grades will be based on the observed laboratory values only, clinical assessments will not be taken into account.

CTCAE Grade 0 will be assigned for all non-missing values not graded as 1 or higher. Grade 5 will not be used.

For laboratory tests where grades are not defined by CTCAE version 5.0, results will be categorized as low/normal/high based on laboratory normal ranges.

The following listings/summaries will be generated separately for hematology and biochemistry tests:

Novartis	Confidential	Page 31 of 43
SAP Amendment 2		Study No. CAAA405A12302

• Listing of all laboratory data with values flagged to show the corresponding CTCAE version 5.0 grades if applicable and the classifications relative to the laboratory normal ranges.

For laboratory tests where grades are defined by CTCAE version 5.0:

- Worst post-baseline CTCAE grade (regardless of the baseline status). Each participant will be counted only once for the worst grade observed post-baseline.
- Shift tables using CTCAE version 5.0 grades to compare baseline to the worst ontreatment value

For laboratory tests where grades are not defined by CTCAE version 5.0:

• Shift tables using the low/normal/high/ (low and high) classification to compare baseline to the worst on-treatment value.

#### 2.8.4 Other safety data

#### 2.8.4.1 ECG and cardiac imaging data

The number and percentage of participants with an abnormal ECG (clinically significant) at screening will be presented. ECG data will be read and interpreted locally. A listing of all ECG assessments will be produced. These analyses will be performed for the FAS.

In addition, for the approximately 10 PK subset participants:

Specified parameters PR, QRS, QT, QTcF, and RR intervals will be obtained from 12-lead ECGs for each participant in the PK subset on treatment day (Day 1) at pre-injection, post-injection/pre-imaging, and post-imaging and at Safety follow-up Day 15.

The number and percentage of PK subset participants with notable ECG values will be presented.

- QT, QTcF
  - New value of > 450 and  $\le 480$  ms
  - New value of > 480 and  $\le 500$  ms
  - New value of > 500 ms
  - Increase from Baseline of  $> 30 \text{ ms to} \le 60 \text{ms}$
  - Increase from Baseline of > 60 ms
- HR
  - Increase from baseline >25% and to a value >100 bpm
  - Decrease from baseline >25% and to a value < 60 bpm
- PR
  - Increase from baseline >25% and to a value >200 ms
  - New value of > 200 ms
- QRS
  - Increase from baseline >25% and to a value > 120 ms
  - New values of QRS > 120 ms

#### 2.8.4.2 Vital signs

Vital sign assessments are performed in order to characterize basic body function. The following parameters were collected: body temperature, blood pressure, pulse rate, respiratory rate.

#### Data handling

Vital signs collected prior to (baseline) and on-treatment (14 + 3 day-window after the study treatment administration) will be summarized. Values measured outside of the on-treatment period will be flagged in the listings.

#### Data analysis

For analysis of vital signs, the clinically notable vital sign criteria are provided in Table 2-3 below.

Vital sign (unit)	Clinically notable criteria	
	Increase	Decrease
Systolic blood pressure (mmHg)	>=180 with increase from baseline of >=20	<=90 with decrease from baseline of >=20
Diastolic blood pressure (mmHg)	>=105 with increase from baseline of >=15	<=50 with decrease from baseline of >=15
Body temperature (°C)	>= 39.1	-
Pulse rate (bpm)	> 100 with increase from baseline of > 25%	< 60 with decrease from baseline > 25%
Respiratory rate	> 22 breaths per minute	<14 breaths per minute

#### Table 2-3 Clinically notable changes in vital signs

The number and percentage of participants with notable vital sign values (high/low) will be presented. Descriptive statistics will be tabulated for baseline, at each post-baseline time point and changes from baseline at each post-baseline time point for each vital sign measure.

A listing of all vital sign assessments will be produced and notable values will be flagged. In the listing, the assessments collected outside of on-treatment period will be flagged.

# 2.9 Pharmacokinetic endpoints

All PK analyses will be carried out on the PAS.

The [F]CTT1057 pharmacokinetic analysis will be performed based on decay-corrected blood radioactivity concentration data obtained by measuring the blood samples drawn at pre-defined time points (Table 8-6 of the protocol) using a calibrated gamma-counting device. Blood mass concentration data were also planned to be summarized per protocol, however the conversion

Novartis	Confidential	Page 33 of 43
SAP Amendment 2		Study No. CAAA405A12302

of radioactivity concentration to mass concentration will not be possible due to missing information of mass concentration of the drug product during the manufacturing process.

Radioactivity concentration in blood will be calculated using the following formula:

$$RDCNNDB = (ACTMENDC / SAMPVOL) / DURSFLT1$$

where, RDCNNDB is radioactivity concentration in blood (not decay corrected), ACTMENDC is radioactivity measured (not decay corrected), SAMPVOL is volume of the sample measured, and DURSFLT1 is gamma counter calibration factor.

Decay correction of the radioactivity concentration in blood will be performed using the following formula:

$$RDCNDCB = RDCNNDB \times e^{-\lambda \cdot (RDACTDAT \& TIM - ECSTDTC)}$$

where, RDCNDCB is radioactivity concentration in blood (decay corrected),  $\lambda$  is decay constant, RDACTDAT&TIM is radioactivity measurement date and time, and ECSTDTC is dose administered date and time.

Decay constant ( $\lambda$ ) is calculated using the following formula:

$$\lambda = \frac{ln^2}{t_{1/2}}$$

where, t1/2 is half-life of 18-F which is 109.7 min.

Blood radioactivity concentration data will be listed by participant and visit/sampling time point. Pharmacokinetic parameters will be listed by participant. Descriptive summary statistics will be provided by visit/sampling time point. Summary statistics will include mean (arithmetic and geometric), standard deviation (SD), coefficient of variation (CV) (arithmetic and geometric), median, minimum, and maximum. An exception to this is Tmax, where only median, minimum, and maximum will be presented.

The following pharmacokinetic parameters will be determined using the actual recorded sampling times and non-compartmental method(s) with Phoenix WinNonlin® (Version 8 or higher): Cmax, Tmax, AUClast, AUCinf, T1/2, Vz and CL (Table 2-4).

 Table 2-4
 Non-compartmental pharmacokinetic parameters

AUC%Extrap 	Area under the plasma concentration-time curve extrapolated from the time t to infinity as a percentage of total AUC (%)
AUClast	The AUC from time zero to the last measurable concentration sampling time (tlast) (mass x time x volume  )
AUCinf	The AUC from time zero to infinity (mass x time x volume  )
Clast 	Last measurable concentration (mass x volume  )
Cmax	The maximum (peak) observed plasma, blood serum, or other body fluid drug concentration

	after single dose administration (mass x volume  )
Tmax	The time to reach maximum (peak) plasma, blood, serum, or other body fluid drug concentration after single dose administration (time)
T 1/2	The elimination half-life associated with the terminal slope ( $\lambda z$ ) of a semi logarithmic concentration-time curve (time)
Tlast 	Last measurable concentration sampling (time)
Rsqadj 	Square of the correlation coefficient associated with lambda_z
CL	The total body clearance (CL) of drug from plasma, blood serum, or other body fluid drug concentration (volume x time  )
Vz	The apparent volume of distribution during terminal phase (associated with $\lambda z$ ) (volume)

 AUC%Extrap and Rsqadj will be used in the interpretation of the primary PK parameters and therefore will be included in the listings only.

 Clast and Tlast will only be listed but not summarized

The elimination of the compound in urine will be evaluated based on decay-corrected urine radioactivity concentration data obtained by measuring the urine samples drawn at pre-defined time points (Table 8-7 of the protocol) using a calibrated gamma-counting device. Urine elimination data will be expressed as the percentage of injected activity (%ID) in each specified time interval and also as cumulative %ID excreted up to the end of each time interval. Urine elimination data will be listed by participants. Descriptive summary statistics will include mean (arithmetic and geometric), SD, CV (arithmetic and geometric), median, minimum, and maximum.

Radioactivity concentration in urine will be calculated using the following formula:

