### 8.5.1 Pharmacokinetics

Pharmacokinetic (PK) samples (blood / urine) will be collected at the visits defined in the assessment schedule (Table 8-6 and Table 8-7) from a subset of approximately 10 participants from the same, singular site.

The number of samples/blood draws and total blood volume collected will not exceed those stated in the protocol.

Blood and urine samples will be counted at the investigational site in an accurately calibrated gamma-counter (e.g. NaI spectrometer) with a suitable reference source of F of known activity counted in the same geometry as that of the biological samples (e.g. 1 mL in a vial).

Information related to the administration of [F]CTT1057, including but not limited to the activity of the dose at the time administration, date and time of dosing, date and time of dose preparation and specific activity at time of dose preparation, must be recorded in the appropriate eCRF page. All samples will be counted locally at the site and the counts per minute (CPM) value will be recorded in the appropriate blood or urine eCRF pages. Well/gamma counter calibration records will be collected from the participating site prior to patient enrollment. Calibrations related information such as date of calibration, calibration factor and background count must be recorded in a dedicated eCRF.

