#### 8.5.1.1 Pharmacokinetic Blood collection and handling

Blood samples will be taken by either direct venipuncture or an indwelling cannula inserted in a forearm vein. At specified time points described in Table 8-6, 1-1.2 mL blood draws will be collected into tubes containing an anticoagulant and gently inverted several times to thoroughly mix the anticoagulant. 1 mL of blood will be transferred into a vial for radioactivity measurement in the well/gamma-counter.

[figure not shown]
All data including but not limited to actual date and time of blood sampling, date and time of measurement by well/gamma-counter, exact volume of sample measured (including any dilutions if applicable) and activity counted by well/gamma counter must be recorded in the appropriate blood collection eCRF page.

[figure not shown]

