# $RDCNNDU = \left(\frac{ACTMENDC}{SAMPVOL}\right) / DURSFLT1$

where, RDCNNDU is radioactivity concentration in urine (not decay corrected), ACTMENDC is radioactivity measured (not decay corrected), SAMPVOL is volume of the sample measured, and DURSFLT1 is gamma counter calibration factor.

Decay correction of the radioactivity concentration in urine will be performed using the following formula:

$$RDCNDCU = RDCNNDB \times e^{-\lambda \cdot (RDACTDAT \&TIM - ECSTDTC)}$$

where, RDCNDCU is radioactivity concentration in urine (decay corrected),  $\lambda$  is decay constant, RDACTDAT&TIM is radioactivity measurement date and time, and ECSTDTC is dose administered date and time.

Decay constant ( $\lambda$ ) is calculated using the following formula:

$$\lambda = \frac{ln^2}{t_{1/2}}$$

Novartis	Confidential	Page 35 of 43
SAP Amendment 2		Study No. CAAA405A12302

where, t1/2 is half-life of 18-F which is 109.7 min.

The percentage of injected activity (%ID) will be calculated using the following formula:

 $PCTINDS = (\frac{RDCNDCU \times SAMPCOL}{ECDOSE \times 1000}) \times 100(\%)$ 

where, PCTINDS is percentage of injected activity (%ID) in urine, and ECDOSE is decaycorrected administered dose (MBq).

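### SAP 2.9 never uses the recorded background count; if the counter readings are gross, T1/2 and AUCinf are biased upward and CL downward

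*SAP*

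**What the plan says.** Protocol 8.5.1 has samples counted locally at one site. For each sample, "the counts per minute (CPM) value will be recorded in the appropriate blood or urine eCRF pages". It adds: "Calibrations related information such as date of calibration, calibration factor and background count must be recorded in a dedicated eCRF". For blood, Protocol 8.5.1.1 uses a second wording: "activity counted by well/gamma counter must be recorded in the appropriate blood collection eCRF page".

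SAP 2.9 gives the blood conversion as "RDCNNDB = (ACTMENDC / SAMPVOL) / DURSFLT1" and defines its terms: "ACTMENDC is radioactivity measured (not decay corrected), SAMPVOL is volume of the sample measured, and DURSFLT1 is gamma counter calibration factor". The urine conversion has the same form: "RDCNNDU is radioactivity concentration in urine (not decay corrected), ACTMENDC is radioactivity measured (not decay corrected"), again divided by volume and calibration factor. Both results are then decay-corrected to the time of dosing. Cmax, Tmax, AUClast, AUCinf, T1/2, Vz and CL are derived from the blood values, and percentage of injected activity from the urine values.

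No background term appears in either formula. SAP section 4, which lists changes from the protocol, explains why mass concentration was dropped but does not mention background.

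**The concern.** The protocol makes three counter quantities available: the sample count, the calibration factor and the background count. The SAP uses the first two. If the sample count still contains background, every concentration carries an added constant that is not tracer.

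That constant does not decay with 18F, while the sample signal does. Its relative share is therefore largest in the late, weak samples, and those determine the terminal slope. T1/2, AUCinf, CL and Vz all depend on that slope. The error is systematic, so averaging over participants does not remove it. Even the pre-dose sample would return a positive tracer concentration.

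**Working it through.** **Is ACTMENDC gross or net?** No sentence in either document says. Two features point to gross counter output. It is divided by a gamma-counter calibration factor, and the urine percentage is formed by dividing by the dose in MBq times 1000, so the calibration step is what turns counts into activity. A background count stored in its own field also makes most sense if it is to be subtracted later. Neither feature is proof.

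**Decay constant.** From "where, t1/2 is half-life of 18-F which is 109.7 min": lambda = ln 2 / 109.7 = 0.006319 per min. The correctly signed factor exp(lambda × t) is 2.13 at 2 h, 3.77 at 3.5 h, 6.66 at 5 h, 9.72 at 6 h and 44.3 at 10 h after dosing.

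**Assumptions for the size.** The documents give no blood curve, counter efficiency or background, and there is no plan figure to reproduce. Assumed:
- terminal intercept 11 kBq/mL with half-life 90, 180 or 300 min
- fast phase of 8 min half-life with intercept 30 or 60 kBq/mL
- 1 mL counted at 40% efficiency, so 1 Bq gives 60 × 0.40 = 24 CPM
- samples at 2.5, 15, 30, 60, 120, 210 and 300 min
- linear trapezoid (first value carried back to time zero), terminal slope from the last three points, no noise

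**One case by hand.** Half-life 90 min, background 300 CPM, each sample counted 1 h after the draw:

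| Draw | True conc. (kBq/mL) | Decay factor at counting | Net CPM | 300 CPM as share |
|---|---|---|---|---|
| 120 min | 11 × 2^(-120/90) = 4.365 | 3.12 | 33,600 | 0.9% |
| 210 min | 11 × 2^(-210/90) = 2.183 | 5.51 | 9,512 | 3.2% |
| 300 min | 11 × 2^(-300/90) = 1.091 | 9.72 | 2,693 | 11.1% |

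The true slope is -ln 2 / 90 = -0.007702 per min. With equal spacing, the fitted slope shifts by [ln(1.1114) - ln(1.0089)] / 180 = +0.000537, giving -0.007164. Apparent T1/2 = 0.6931 / 0.007164 = 97 min instead of 90. CL falls by 2.0% to 2.4%, depending on the fast phase.

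**Range over the assumed curves, correctly signed decay correction:**

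| Counting | Background (CPM) | CL with 5 h sample | CL without it |
|---|---|---|---|
| 1 h after draw | 100 | -0.6% to -1.1% | -0.4% to -0.6% |
| 1 h after draw | 300 | -2.0% to -3.3% | -1.1% to -1.9% |
| 1 h after draw | 1000 | -6.7% to -10.8% | -3.5% to -6.2% |
| all at 10 h | 300 | -10.1% to -13.9% | -9.2% to -11.6% |

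With no fast phase at all, the 300 CPM prompt-counting bound is -3.5%, so about -0.4% to -3.4% is a fair summary for 100-300 CPM. AUCinf rises correspondingly, since CL is dose divided by AUCinf. At 300 CPM with prompt counting, T1/2 rises by 4% to 8% with the 5 h sample and by about 2% without it. Subtracting the background returns every case to the true value.

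**Interaction with the printed decay sign.** SAP 2.9 prints a negative exponent with measurement time minus dose time. With a constant counting delay this shortens the apparent half-life to 1 / (1/T + 2/109.7). A true 240 min becomes 1 / (0.004167 + 0.018232) = 44.6 min. Under that sign, 300 CPM with prompt counting changes CL by only about 0.3% and T1/2 by 1 min or less.

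**The case against.** A reader might infer that the SAP's PK results will be biased. The documents do not support that. ACTMENDC may already be net, for instance if the counter subtracts background automatically; then there is no bias, and a second subtraction would create one in the other direction. This objection stands, and the point is conditional for that reason.

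A reader might also infer that T1/2 and AUCinf computed from SAP 2.9 as printed would come out too high. They would not, under prompt counting: the negative exponent is a separate and larger error that pushes them down. The background effect matters once that sign is put right.

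The recorded background may be a calibration-time value rather than one from each counting session, since the protocol lists it with the calibration date and factor. Some figures and the urine sampling table are missing from the public text, so counting instructions may exist elsewhere. Both are reasons to ask the site before choosing a value to subtract.

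The double-digit CL changes at 300 CPM require counting everything at 10 h, which nothing in the documents suggests. The 5 h draw is optional, and without it the prompt-counting effect roughly halves. All of this stands. It limits the size, but it does not supply the missing definition: the SAP states an explicit formula, and applied to gross counts that formula is wrong.

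**Conclusion.** The concern holds in conditional form. SAP 2.9 gives the mandatory background count no use and does not say whether ACTMENDC is gross or net. If gross, the direction under correctly signed decay correction is T1/2 and AUCinf up and CL down.

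With prompt counting and 100-300 CPM, the assumed curves give a CL change of about -0.4% to -3.4%, with larger changes at higher background or long counting delays. These sizes rest entirely on the assumed curve, efficiency, background and delay. Urine excretion would be overstated by the same mechanism, but that is not sized here because no urine volumes or count rates are given.

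The scope is a descriptive secondary endpoint in about 10 participants, with no test or threshold attached. Patient-level sensitivity and region-level specificity are unaffected. It is worth correcting because it is cheap and the concentrations cannot otherwise be reproduced unambiguously.

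**What to change.** Ask the single PK site whether the CPM entered in the eCRF is gross or net, and whether the recorded background comes from the counter used for the samples.

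- If gross: change both formulas in SAP 2.9 to ((ACTMENDC - background) / SAMPVOL) / DURSFLT1, with background in the same units and from the same counter. Treat non-positive net counts as below quantification.
- If net: state this in the definition of ACTMENDC and do not subtract again.

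Make the change together with the separate correction of the decay-correction sign, because the two act on the same values. The cost is one query to one site, a sentence in the SAP and, if gross, one term in the program. The background count is already a required eCRF field.
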